7.3 ANALYSIS OF STUDY CONDUCT

All patients randomized into the study will be summarized by treatment group as randomized. The randomization stratification factors will be listed and tabulated as recorded in the IVRS by treatment group as randomized.

The number of patients who are in the ITT and SAFETY populations will be summarized by treatment group and overall.

Study treatment administration, duration of follow-up, discontinuation from study treatment and the reasons for discontinuation will be summarized by treatment group for all randomized patients. In addition, major protocol deviations and eligibility violations will also be summarized by treatment group. Protocol violations for this study include, but are not limited to, the following:

- Failure to meet inclusion/exclusion criteria
- Use of a prohibited concomitant medication
- Dose modifications that are not within the protocol specifications
- Any other deviation that presents significant risk or safety concerns to the patient

7.4 ANALYSIS OF TREATMENT GROUP COMPARABILITY

The evaluation of treatment group comparability between the 2 treatment groups will include summary of demographics, baseline disease characteristics, medical history, and patient treatment history.

Descriptive statistics (mean, standard deviation, median, range) will be presented by treatment group for continuous variables such as age and time from initial diagnosis. Categorical variables will be summarized using frequencies and percentages.

7.4.1 Demographics and Baseline Characteristics

The following parameters will be summarized overall by treatment group as randomized for all patients in the ITT population: Age, race, ethnicity and baseline weight and height.

ARN-509-003 Statistical Analysis Plan v7.0 26 June 2017

Page 9 of 34

7.4.2 Disease Characteristics and Prior Therapy

The following parameters will be summarized overall by treatment group as randomized for all patients in the ITT population:

- ECOG performance status
- Baseline PSA value and PSA Doubling Time (PSADT)
- Time (months) from initial diagnosis of prostate cancer to randomization
- Total Gleason Score at initial diagnosis
- Tumor stage at initial diagnosis
- Lymph nodes stage at initial diagnosis
- Number of prior hormonal therapies
- Use of bone-sparing agent (Yes/No) at baseline
- History of surgical prostate cancer procedures (Yes/No)
- Type of surgical procedures (prostatectomy, orchiectomy, transurethral resection of the prostate (TURP), and other)
- History of radiotherapy (Yes/No)
- Type of radiotherapy
- History of prior adjuvant/neoadjuvant chemotherapy (Yes/No)

7.4.3 Study Drug Administration

The SAFETY population will be used to summarize drug exposure, treatment compliance, and dose modifications by treatment group as treated.

Treatment duration will be defined as the duration of time from the date of the first dose of study drug to the date of last dose of study drug + 1 day.

The total cumulative dose in milligrams (mg) will be calculated as 30 or 60 mg multiplied by the number of capsules or tablets taken. The number of capsules or tablets taken will be calculated based on the number of capsules or tablets dispensed at the study visits minus the number of capsules or tablets indicated as having been returned.

The overall treatment compliance will be defined as the total dose in mg taken during the study divided by the expected total dose in mg. A subject's expected total dose will be calculated as the assigned dose per day multiplied by treatment duration. Each patient should be taking 8 capsules or 4 tablets per day maximum while on the study. For patients with dose reductions, the expected number of capsules or tablets will be reflective of the new dose with a reduced number of total capsules or tablets.

Dose reduction or interruption and the reason for the dose reduction or interruption will be summarized by treatment group as treated.

ARN-509-003 Statistical Analysis Plan v7.0 26 June 2017

Page 10 of 34

7.4.4 Pre-study and Concomitant Medications

Concomitant medications and medications taken prior to starting study treatment will be summarized for all patients in the SAFETY population by treatment group as treated. Medications are considered concomitant if taken during the treatment-emergent period. Prior medications are medications with the start date and/or end date before study drug date. Medications will be summarized by WHO Drug therapeutic class and generic medication name.

7.4.5 Subsequent Anti-Cancer Therapy

Subsequent systemic anti-cancer therapy taken after the patient has discontinued study drug will be summarized by treatment group and overall. Medications will be summarized by WHO Drug therapeutic class and generic medication name.

7.5 EFFICACY ANALYSES

The following section outlines the planned analyses of the primary and secondary efficacy outcomes of the study.

Efficacy analyses will be performed on the ITT population, incorporating the randomization stratification factors as documented on the IVRS, unless otherwise specified.

Time-to-event endpoints will be summarized using the Kaplan-Meier method ³ and displayed graphically where appropriate. Median event times and 2-sided 95% confidence interval for each median will be provided. Cox proportional-hazard models, including the stratification factors at baseline, will be used to estimate the hazard ratio (HR) and its 95% confidence interval (CI).

Response endpoints (eg, PSA response rate) will be summarized using descriptive statistics for categorical data by treatment group. The relative risk (treatment:control) will be reported along with the associated 2-tailed 95% CIs. The two treatment groups will be compared using the stratified Mantel-Haenszel test; Fisher's exact test may be used if the expected counts in some cells are small.

7.5.1 Blinded Independent Central Review (BICR)

Analyses of efficacy endpoints which are based on radiographic tumor assessments (MFS, TTM, and PFS) will be based on the results of the blinded independent central review (BICR), provided via electronic data transfer by the third-party core imaging laboratory.

All scans will be submitted for independent review of disease progression during the study according to an Independent Review Charter to be prepared by the core imaging laboratory in consultation with the Sponsor.

7.5.2 Primary Endpoint (MFS)

The primary efficacy endpoint is metastasis-free survival (MFS), defined as the time from randomization to first evidence of BICR-confirmed radiographically detectable bone or soft tissue distant metastasis (simply referred to as "metastasis" from this point forward) or death due to any cause (whichever occurs earlier) + 1 day.

ARN-509-	-003					
Statistical	Analysis	Plan	v7.0	26.	June	2017

Page 11 of 34

MFS data for patients without metastasis or death will be censored on the date of the last tumor assessment (or, if no tumor assessment was performed after the baseline visit, at the date of randomization + 1 day).

Additional censoring rules will vary according to whether the analysis is performed for US or ex-US regulatory purposes, as follows; both results will be provided in the clinical study report.

Scenario	US regulatory guidance	ex-US regulatory guidance ⁴
Data from patients who are lost to follow-up or whose disease progression (development of metastasis) or death occurs after 2 or more consecutively missing or unevaluable tumor assessments	Censored on the date of the last tumor assessment that the patient was known to be metastasis-free	Time of progression will be determined using the first date when there is documented evidence of progression or death (whichever occurs earlier) regardless of missed or unevaluable tumor assessments
Patients that receive new systemic anti-cancer therapy prior to documented disease progression (development of metastasis) or death	Censored on the date of the last tumor assessment prior to the start of the new systemic anti-cancer therapy	Time of progression will be determined using the first date when there is documented evidence of progression or death (whichever occurs earlier) regardless of change of therapy

Disease progression (development of metastasis) will be assessed by an independent core imaging laboratory using the Response Evaluation Criteria in Solid Tumors (RECIST v1.1).⁵ The appearance of new (or distant) metastatic lesions denotes disease progression. For new bone lesions detected on bone scans, a second imaging modality (e.g., CT or MRI) will be required to confirm progression.

The primary efficacy analysis will be completed when approximately 372 MFS events have occurred. The primary analysis will compare the MFS distributions in the two treatment groups using a two-sided log-rank test, stratified by PSADT (≤ 6 months vs. > 6 months), the use of a bone-sparing agent (Yes vs. No), and the presence of loco-regional disease (N0 vs. N1) at the 0.05 significance level. The non-stratified log-rank test will be provided as a sensitivity analysis. Additional sensitivity analyses are provided in Section7.8

7.5.3 Secondary Endpoints

Time-to-event-based secondary endpoint analyses (OS, time to symptomatic progression, time to initiation of cytotoxic chemotherapy, progression-free survival, and time to metastasis) will be performed using a two-sided stratified log-rank test. Non-stratified log-rank tests will be provided as sensitivity analyses for OS.

ARN-509-003 Statistical Analysis Plan v7.0 26 June 2017

Page 12 of 34

For ease of notation, in the sequel, time to symptomatic progression is abbreviated as "SymProg" and time to initiation of cytotoxic chemotherapy is abbreviated as "CytoChemo". A hierarchical adaptive group sequential procedure will be used to test the secondary endpoints (Figure). The method allows re-estimation of the number of events necessary for the next best opportunity to achieve the desired conditional power. The method controls the familywise type I error rate for the primary and all secondary endpoints.

Figure 1: Hierarchical Adaptive Group Sequential Procedure

IA=interim analysis; FA=final analysis

Specifically, a hierarchical testing will be performed in the following order: TTM, PFS, SymProg, OS, and CytoChemo, each at alpha=0.05 (2-sided). As depicted in Figure 1, each endpoint will have a final analysis (FA) but there will be no interim analysis (IA) for TTM and PFS, 1 IA for SymProg, and up to 2 IAs for OS and CytoChemo. The testing of SymProg, OS and CytoChemo endpoints will utilize an adaptive group sequential method, according to the pre-specified O'Brien-Fleming (OBF)-type alpha spending function⁶ with possible re-estimation of the required number of events necessary for the next analysis to maintain the desired conditional power. If SymProg is significant at the IA, then there will be only 1 IA for OS and CytoChemo (ie, with "IA #2" boxes removed from Figure 1); otherwise there will be 2 IAs for OS and CytoChemo.

ARN-509-003 Statistical Analysis Plan v7.0 26 June 2017

Page 13 of 34

The FA of TTM and PFS, IA of SymProg, and the first IAs of OS and CytoChemo will all be performed at the same time as the primary analysis of MFS (approximately 372 events). At the time of the MFS analysis, testing of the SymProg, OS and CytoChemo endpoints will be carried out using the OBF-type alpha spending function and nominal p-values will be provided.

Assuming that the primary test for MFS is significant at alpha=0.05, TTM will then be tested at alpha=0.05. If significant, then PFS will be tested at alpha=0.05. If PFS is significant, then the Sponsor will perform the IA for SymProg. Assuming HR=0.75 for SymProg, then 427 events are required to yield 80% power at alpha=0.05. Suppose that *X1* events will have accumulated at the IA for SymProg, the information fraction would be t=X1/427. Efficacy of SymProg will be concluded if the stratified log-rank test statistic exceeds the critical value derived from the OBF-type alpha spending function.

The SymProg events re-estimation will be based on a conditional power of 90% for the next stage, calculated using the observed HR. Note that because of the variability associated with the observed HR, a conditional power of 90% is used in order to maintain an overall power of approximately 80% if the true HR is 0.75. The recommended number of SymProg events for the FA should be in the range of 191 (additional 191-XI events set as the minimum required for the next stage) to XI+(427-XI)*1.1 (not more than 10% increase on the preplanned number of events for the next stage). Because the true HR for SymProg is unknown, the minimum number of 191 is chosen to yield at least 80% power to detect an HR of 0.65 at an alpha level of 0.05.

The SymProg events re-estimation will be performed by the independent statistician who supports the IDMC activities. The dissemination and review of the specific results of the IA will be limited to the IDMC.

In order to maintain a strong control of the type I error rate for the SymProg analysis, an inverse normal p-value combination method will be used as the final test.⁷ The inverse normal p-value combination method allows flexible adaptations at an IA and creates a valid test that controls the type I error rate in a strong sense analytically. In this proposed design the adaptation is the potential adjustment of the required number of events for the next stage.

The final test statistics for the null hypothesis H₀: HR for SymProg ≥ 1 is defined as

$$Z = w_1 F^{-1} (1 - p_1) + w_2 F^{-1} (1 - p_2),$$

where $F^{-1}(x)$ is the inverse of the standard normal cumulative distribution function, $w_1 = \sqrt{t}$, $w_2 = \sqrt{1-t}$, p_1 denotes the first stage p-value and p_2 denotes the second stage p-value.

Critical values for success are calculated based on the OBF-type alpha spending function. The study may be stopped early for efficacy if the interim test statistic exceeds the first stage critical value z_1 , or stops for success at the second stage, if the final test statistic exceeds the second stage critical value z_2 . Therefore, the null hypothesis H₀ will be rejected either at the first analysis if $F^{-1}(1 - p_1) > z_1$, or at the FA if $Z > z_2$.

The adaptive group sequential testing of OS and CytoChemo will be similar to that of SymProg as described above, except that there is a possibility of 1 more IA to be incorporated in the inverse normal p-value combination method. Due to the hierarchical

ARN-509-003	
Statistical Analysis Plan v7.0 26 June 2017	Page 14 of 34

structure of the testing procedure, an outline of some additional technical details is provided in Appendix 1.

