### **3.1.1 Crossover Option in the Event of Unblinding**

At the time of study unblinding and in the event of a positive study result, all subjects currently receiving placebo will have the opportunity to receive active therapy with apalutamide (refer to Appendix 10).

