**APPENDIX 10: CROSSOVER TO OPEN LABEL APALUTAMIDE AFTER STUDY UNBLINDING**

At the time the decision is made to unblind the study, investigators will be notified by the sponsor. Subjects randomized to placebo who are currently on study treatment will be offered treatment with open-label apalutamide at 240 mg/day.

Subjects previously randomized to apalutamide will continue on protocol and follow the current schedule of activities (Appendix 1, with modifications below) and will be given open-label apalutamide.

For subjects who crossover from placebo to apalutamide, radiographic scans will no longer be required for the study and submitted for blinded central independent review. Subjects will be followed for progression per Investigator decision including symptoms, radiographic scans or PSA. PSA data submitted to the central laboratory will no longer be blinded. In addition, for all subjects, PK samples will no longer need to be collected at the time of unblinding.

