 - ✓ The OBF-type alpha spending will apply to OS and CytoChemo at the IA for SymProg, the weight w1 is determined for each of them and the corresponding p-values calculated to be used later by the combination test. However, significance of either OS or CytoChemo could not be claimed even if the efficacy boundary is crossed for either of them at this time. The study proceeds to the FA for SymProg determined by the 90% conditional power on SymProg. The required adjustment for SymProg: use p-value combination test with the prefixed w1 and w2=sqrt(1-w1^2).
 - If SymProg is not significant at FA, the study stops. No testing and next stages for OS/CytoChemo are possible.
 - ➢ If SymProg is significant at FA
 - Test OS at the FA for SymProg at significance level alpha(t2), where t2=0.8 is the proportion of projected OS events at this time over the pre-planned maximum number of OS events.
 - If OS is not significant at the FA for SymProg, then the timing of the FA for OS is determined by the 90% conditional power on OS. The OBF-type alpha spending will apply to CytoChemo at the FA for SymProg, the weight w2=sqrt(t2-t1) is determined and the corresponding p-value calculated to be used later by the combination test, where t2=0.66 is the proportion of projected CytoChemo events at this time over the preplanned maximum number of CytoChemo events. However, significance of CytoChemo could not be claimed even if the efficacy boundary is crossed at this time. The study proceeds to the FA for OS.
 - If OS is significant at FA, then CytoChemo will be tested at the time of FA for OS, and if this is also significant, the study stops with superiority established on all endpoints. Otherwise, the study stops with superiority established on all endpoints except CytoChemo. The required adjustment at FA for OS and CytoChemo: use

ARN-509-003 Statistical Analysis Plan v7.0 26 June 2017

Page 27 of 34

p-value combination test with the weights w1=sqrt(t1) and w2=sqrt(t2-t1), and $w3=sqrt(1-w1^2-w2^2)$.

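### SAP 7.5.3 says event re-estimation keeps power near 80% for symptomatic progression at HR 0.75; the rule as specified gives about 71–77% if the interim falls below 191 events

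*SAP*

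**What the plan says.** SAP 7.5.3 tests time to symptomatic progression third among the secondary endpoints, with one interim and one final analysis. The interim has a fixed place: "IA of SymProg, and the first IAs of OS and CytoChemo will all be performed at the same time as the primary analysis of MFS". The preplanned total is 427 events (80% power at HR 0.75, two-sided 0.05), and the information fraction is X1/427, where X1 is the interim event count. No value of X1 is given.

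If the interim is not significant, the final event number is reset: "The SymProg events re-estimation will be based on a conditional power of 90% for the next stage, calculated using the observed HR". Two limits apply. The lower is a total of 191 ("additional 191-XI events set as the minimum required for the next stage"), chosen for at least 80% power at HR 0.65. The upper is X1 + 1.1 × (427 − X1) ("not more than 10% increase on the preplanned number of events for the next stage"). The final test is an inverse-normal combination with fixed weights and O'Brien-Fleming-type spending.

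The SAP gives the purpose of the 90% target: "a conditional power of 90% is used in order to maintain an overall power of approximately 80% if the true HR is 0.75". It shows no calculation for this and no conditional-power formula.

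**The concern.** A rule that can remove many events after a favourable interim, but add few after an unfavourable one, would be expected to lose power against the fixed 427-event design. The SAP says power is held. If it is not, the stated chance of missing a true HR of 0.75 (about 20%) is too low.

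This endpoint also gates overall survival and chemotherapy. When the interim is not significant, SAP Appendix 1 says: "If SymProg is not significant at FA, the study stops. No testing and next stages for OS/CytoChemo are possible". A miss at the final analysis therefore ends testing of both.

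A second question is what the figure assumes about treatment after the interim. Protocol 3.1.1 provides: "At the time of study unblinding and in the event of a positive study result, all subjects currently receiving placebo will have the opportunity" for apalutamide treatment. The SAP does not mention this crossover.

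**Working it through.** **Inputs.** From SAP 3 and 7.5.3 and Appendix 1: 2:1 randomisation, two-sided alpha 0.05, 427 planned events, t = X1/427, 90% conditional power at the observed HR, total limited to 191 through X1 + 1.1 × (427 − X1), weights √t and √(1 − t). Assumed: X1 from 30 to 190, because the additional-events minimum of 191 − X1 is positive only if X1 is below 191.

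**The plan's own figures.** Under 2:1 allocation the information is 2/9 per event.

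- HR 0.75: (1.960 + 0.842)² / [(2/9)(ln 0.75)²] = 7.849/0.01839 = 426.8, so 427 events; power 80.0%.
- HR 0.65: 7.849/0.04124 = 190.3, so 191 events; power 80.1%.

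Both reproduce. With the interim included but no re-estimation, a total of 427 keeps 79.9–80.0% for X1 = 40–190.

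**Spending function.** The protocol's amendment history gives an alpha spend of 0.0012 at 243 of 526 deaths under alpha 0.04. The O'Brien-Fleming-type form used here gives 0.00124 there. At X1 = 120 the critical values are 4.07 and 1.96. The other common form (4.07 becomes 3.70) changes power by less than 1 point.

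**Re-estimation.** With θ = −ln(observed HR), Z1 = θ√(2·X1/9) and final critical value z2, the second stage must exceed

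c = (z2 − √t·Z1)/√(1 − t),

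and conditional power with D further events is Φ(θ√(2D/9) − c). Setting this to 90% gives D = [(c + 1.282)/θ]² × 9/2.

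At X1 = 120, t = 0.281 and the upper limit is 120 + 1.1 × 307 = 457:

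| Observed HR | Z1 | c | D needed | Total needed | Total used |
|---|---|---|---|---|---|
| 0.60 | 2.64 | 0.66 | 66 | 186 | 191 (minimum) |
| 0.65 | 2.22 | 0.92 | 118 | 238 | 238 |
| 0.75 | 1.49 | 1.38 | 387 | 507 | 457 (maximum) |

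The total needed equals 427 at an observed HR of about 0.731 (Z1 = 1.615). If the true HR is 0.75, Z1 has mean 1.486, so the chance of a total below 427 is P(N > 0.13), about 45%. Even an observed HR equal to the design value hits the maximum.

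**Overall power at true HR 0.75, no crossover** (400,000 simulated interims per X1; observed HR of 1 or more goes to the maximum):

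| X1 | Rule as written | Minimum raised to 350 |
|---|---|---|
| 30 | 70.5% | 79% |
| 60 | 72.4% | 80% |
| 80 | 73.2% | 80% |
| 120 | 74.4% | 80% |
| 150 | 75.2% | 80% |
| 190 | 77.0% | 80% |

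Power reaches 80% at about X1 = 275. Across X1 = 30–190, 41–46% of second stages finish below 427 events. Simulated one-sided type I error is 0.025. At X1 = 120, minimums of 191, 250, 300, 350 and 427 give 74.4, 76.5, 78.3, 79.9 and 82.0%.

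**The case against.** **The formula is not given.** If the 90% is read as the stand-alone power of the second stage, ignoring the first-stage result, the rule gives about 77% at X1 = 80, 80% at 120 and 82% at 190. That would match the SAP's sentence over much of the plausible range. It is not what conditional power normally means for a combination test, but the SAP does not exclude it. This stands as a reason to ask for the formula.

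**X1 is unknown, and the size depends on method.** Fair. The 71% end needs a very early interim; for X1 = 80–190 the range is 73–77%. A patient-level log-rank simulation gives 74–79% for X1 = 60–190, but the fixed 427-event design reaches 81–83% in that simulation, so a loss of about 4–7 points remains.

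**The 191 minimum is deliberate.** It is. The rule has 92–96% power at HR 0.65 for X1 = 30–190, and an earlier final analysis has value. Giving up some power at HR 0.75 for it is a legitimate choice. That defends the rule, not the sentence saying power is kept.

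**Crossover.** A reader might infer that crossover will certainly dilute the second stage, and by a known amount. The documents do not support this. Protocol 3.1.1 requires both unblinding and a positive result, and does not say which result. Protocol 5.2 releases the codes only after study completion and database lock. SAP 7.5.3 confines the specific interim results to the IDMC. The offer is also limited: "Subjects randomized to placebo who are currently on study treatment will be offered treatment with open-label apalutamide at 240 mg/day", and Appendix 10 excludes men with an end-of-treatment visit and centrally confirmed metastasis. No crossover share is given, so any diluted power figure would rest on invented inputs. What stands is that the power statement is silent on crossover, and that crossover before the final analysis could only lower the figure if apalutamide works.

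**Conclusion.** The stated overall power is too high for the rule as specified. At a true HR of 0.75 it is about 71–77% for X1 = 30–190, so the chance of a miss is about 23–29% rather than about 20%. This assumes conditional power computed for the combination test, proportional hazards, no crossover, and X1 below 191. The shortfall fades as the interim moves later and is gone near X1 = 275.

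A reader might go further and conclude that the test is invalid or that the 191 minimum must be raised. Neither follows. The fixed-weight combination test controls type I error, and the minimum has a stated rationale. The error is in a planning statement about the third-ranked secondary endpoint. It deserves correction because that endpoint controls access to the survival test.

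**What to change.** In SAP 7.5.3:

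1. State the conditional-power formula, including whether it uses the weighted combination statistic.
2. Replace the 80% figure with the power the rule delivers by X1: about 71–77% for X1 below 191, or a short table.
3. Add that this assumes no placebo crossover before the final analysis, and that crossover under Protocol 3.1.1 would lower it by an amount not fixed in advance.

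These are text changes; the test, boundaries and event limits stay as they are.

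If the sponsor would rather keep the 80% statement, a minimum of about 350 events, with the maximum and the 90% target unchanged, gives 79–80% for X1 = 30–190. The price is a later final analysis. At X1 = 120, mean final events when a second stage is run rise from about 369 to 412 at HR 0.75, and from about 297 to 382 at HR 0.65, where power goes from 93% to 98.5%. Where the present rule would stop at 191, the wait is 350 − 191 = 159 events longer. That is an option to weigh, not a required change.
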